The short-term impact of Botulinum Neurotoxin-A on muscle morphology and gait in children with spastic cerebral palsy

NCT number: NCT05126693

Protocol date: May 10, 2022

Study protocol

This study will include participants of two different projects. Both projects are approved by the local ethics committee of the University Hospitals Leuven, Belgium (s59945 TAMTA project, s62187 and s62645 3D-MMAP project) (Ethische Commissie Onderzoek KU Leuven/UZ Leuven). Written informed consent will be obtained from the parents or legal guardian. Participants will be included between May 2019 and June 2022.

Participants

Children aged between 3-11 years, GMFCS levels I-III with SCP, scheduled for BoNT-A in the MG and/or ST, as part of a multilevel treatment, will be included. Participants will be recruited via two parallel prospective studies. Both studies will investigate the effect of integrated BoNT-A treatment on muscle morphology and gait, while one study will also evaluate the effects on spasticity (s59945 TAMTA project). The selection criteria for the participants are similar in both studies. The exclusion criteria are: any signs of dystonia or ataxia in the lower limbs, severe muscle weakness or poor selectivity in the plantar flexors or knee flexors and cognitive problems that would impede the measurements, intrathecal baclofen pump, previous muscle surgery in the lower limbs or selective dorsal rhizotomy, previous bony corrections in the lower limb within two years before assessments, previous BoNT-A treatment within six months before the baseline assessment or within six months before the pre-BoNT-A 3DGA. Additionally, the physical therapy frequency has to be consistent for at least three months before inclusion. The participants will be measured twice, before and 8-10 weeks after BoNT-A treatment, to evaluate the short-term effects. All children (of both studies) will receive 3DfUS assessments and a 3DGA with clinical examination of the lower limbs. A subset of children (i.e. the participants of one of the two studies) will undergo an additional instrumented spasticity assessment in order to evaluate the BoNT-A-induced tone reduction. During the follow-up, all children will receive usual care including intensive physical therapy, orthotic management, and oral tone reduction if needed.

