An age- and functional severity-matched (group-matching based on age and GMFCS level) control group, meeting the same inclusion criteria as the intervention group, but not receiving any intervention apart from their usual care, will be included. The participants of the control group will be recruited via Cerebral Palsy Reference Center of the University Hospitals Leuven, Belgium and the Inkendaal Rehabilitation Hospital Vlezenbeek, Belgium. All children eligible for inclusion will be measured, however the final data selection will be based on accurate matching with the participants in the intervention group. The participants in the control group will undergo 3DfUS measurements only, with an interval of 8-10 weeks between the two assessments.

Procedure

The most affected leg, based on the most recent clinical examination (highest modified Ashworth score for the ankle and knee joints), will be assessed. Measures of body mass, height, total leg length and lower leg length will be taken. A standardized anamnesis will be performed to request treatment history and usual care details.

Muscle selection for BoNT-A injection will be primarily based on the most recent clinical examination and multidisciplinary evaluation of the 3DGA data. BoNT-A, Onabotulinum toxin A (Botox®, Allergan) injections will be applied by a pediatric orthopedic surgeon under general (mask) anesthesia, guided by ultrasonography or palpation. A dose of 100 units of BoNT-A will be diluted in 5ml of saline. The BoNT-A dilution will be injected at multiple sites, in areas with the largest concentration of motor endplates in the muscles selected for treatment. A maximum of 50 units will be injected per site. BoNT-A is suggested to be more effective when part of an integrated approach, i.e., combined with casting, orthotic wear and physical therapy. Therefore, lower leg casts and removable upper leg casts will be applied as indicated.

All additional study assessments (3DfUS, clinical examination, instrumented spasticity assessment and 3DGA) will be performed by three trained assessors. The pre- and post-assessments will always be performed by the same assessor.

Assessments

1. Muscle morphology

Muscle morphology of the MG and distal compartment of the ST muscle will be assessed by 3DfUS. This technique, combining B-mode ultrasonography with three-dimensional motion tracking, is proven valid and reliable in muscle morphology assessments in children with SCP in previous studies.

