Ultrasound assessments will be performed while the participant will be placed in prone position. The lower leg will be supported by a triangular cushion to allow slight knee flexion (approximately 25 degrees) and avoid bi-articular stretch on the MG and ST. The ankle will be in resting position without fixation. The joint angles will be measured by goniometry.

Large amounts of acoustic transmission gel will be used to assure smooth movement of the transducer and optimal contact between the transducer and skin. An additional curved gel pad, the Portico, will be used to reduce muscle deformation during the acquisition. Muscle images will be recorded by Stradwin software (version 6.0; Mechanical Engineering, Cambridge University, Cambridge, UK) while moving the transducer from muscle origin to tendinous insertion. The acquisitions will be repeated in case of bad quality images, movement or muscle contraction or when the bony landmarks or muscle borders are missed.

After data collection, the muscle images will be processed by a trained assessor using the Stradwin software (version 6.0; Mechanical Engineering, Cambridge University, Cambridge, UK). Muscle volume (in millimeters) will be estimated by the cubic planimetry technique based on segmentations that will be manually drawn along the inside of the muscle borders in 5-10% of the transverse 2D muscle images. Additionally, echogenicity intensity, as a proxy of muscle quality, will be based on the average of the interpolated reconstruction of the muscle and will be expressed as a gray value on an 8-bit scale (values between 0-255), whereby higher values (whither images) will indicate reduced muscle quality. Muscle belly lengths will be calculated as the Euclidean distance between the muscle origin (MG: posterior surface of medial femoral condyle, ST: ischial tuberosity) and the muscle-tendon junction. The tendon length of the MG will be calculated between the muscle-tendon junction and tendinous insertion. The MTU length of the MG will be calculated by adding the muscle belly to the tendon length.

In order to compare children with different body dimensions, muscle volume will be normalized to the product of body mass*height, and muscle and tendon lengths will be expressed as a percentage of total leg length.

The absolute muscle-specific growth rates for muscle volume during the period between the two assessments will be calculated by the following formulas:

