Normality of data distribution will be checked by a Kolmogorov-Smirnov test ($p < 0.05$). When most parameters are not normally distributed, non-parametric statistical tests will be performed.

Participant characteristics, maximal dorsiflexion angle (measured with the knee extended), popliteal angle (unilateral), and normalized muscle morphology parameters of the intervention and control group will be compared at baseline by a Mann-Whitney U test.

A Wilcoxon signed rank test will be used to evaluate (within) treatment effects in muscle morphology, instrumented spasticity assessment outcomes, spatial-temporal parameters of the 3DGAs ($\alpha = 0.05$). A Bonferroni correction will be applied for the gait kinematic parameters per joint (ankle: $\alpha = 0.05/4 = 0.0125$, knee: $\alpha = 0.05/3 = 0.0167$). Gait parameters will be considered meaningful if statistically significant changes will be noted that are exceeding the SEM or MCID.

Additionally, median difference scores ($x_{\text{post}} - x_{\text{pre}}$) for muscle morphology parameters will be calculated in both the intervention and control group and between-group differences were tested by a Mann Whitney-U test. Additionally, the changes will be expressed as a percentage change of the baseline values for both groups.

Paired t-tests of the ankle and knee kinematics over the entire gait cycle using SnPM analysis will be performed to identify treatment-induced changes in these sagittal plane motions. The averaged ankle and knee kinematic waveforms, consisting of 101 points will be imported to the SPM1d software (version 0.4, available for download at <http://www.spm1d.org/>) in Matlab (The MathWorks, Natick, MA, USA, version 2020b). Clusters will be formed if the critical threshold, based on random field theory, will be crossed ($\alpha = 0.05$). In case of significant clusters, the p-value, details on the location and the duration (percentages of the entire gait cycle) will be reported. Clusters will be considered meaningful when their duration was exceeding 3% of the gait cycle and whether the differences between the means of the pre- and post-BoNT-A joint kinematics will be exceeding the respective SEMs.

References

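### Section 5 tests treatment effects on muscle morphology with an uncontrolled pre/post test and gives the planned comparison with the control group no priority

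*Combined protocol and SAP*

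**What the plan says.** Section 5 plans two analyses of muscle morphology.

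- **Within group.** "A Wilcoxon signed rank test will be used to evaluate (within) treatment effects in muscle morphology", with alpha 0.05. The control group plays no part in this test.
- **Between groups.** Post-minus-pre difference scores are calculated in both groups, and "between-group differences were tested by a Mann Whitney-U test". No alpha is attached to this test, and it is not ranked against the first.

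The design supports the second analysis. Under Participants, the controls are group-matched on age and GMFCS level and are described as "not receiving any intervention apart from their usual care". "The participants in the control group will undergo 3DfUS measurements only", and their two scans are 8 to 10 weeks apart, the same follow-up as for the treated children.

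Under Assessments, 1. Muscle morphology, the primary outcomes are normalized volume, echogenicity intensity and absolute volume growth rate. No deciding contrast is named there. Section 5 says when a change in a gait parameter or a waveform cluster counts as meaningful, but has no such rule for morphology.

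**The concern.** The entry criterion is "Children aged between 3-11 years", so the muscles may change over 8 to 10 weeks without any injection. In the same interval "all children will receive usual care including intensive physical therapy, orthotic management, and oral tone reduction if needed". A signed rank test in the treated group asks only whether the typical change is zero. It cannot attribute a change to treatment rather than to growth, usual care or repeat measurement.

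The plan describes this test as evaluating treatment effects and does not say what follows if it disagrees with the comparison against controls. An analyst following the plan could therefore report change that both groups share as an effect of treatment. The error can also run the other way: a treatment that offsets normal growth could leave no pre/post change to detect.

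The growth rate needs a separate word. It is one value per child, the change in volume divided by months elapsed, so it has no pre and post pair. Section 5 names no test for it. A one-group test could ask only whether growth differs from zero.

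**Working it through.** **Figures in the plan.** There is no sample size, SD, power or expected change for morphology, so there is no stated figure to reproduce. The only computed figures in section 5 are the Bonferroni levels, 0.05/4 = 0.0125 and 0.05/3 = 0.0167. Both are correct, and both concern gait.

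**Inputs from the documents.** Signed rank test on pre/post data in the treated group at 0.05; Mann-Whitney test on change between groups.

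**Assumptions.** Normally distributed changes with SD 1; equal groups; two-sided tests at 5% (sidedness is not stated); 14 to 40 children per group. The only sample size in the document is 14, for the spasticity subset. Drift *d* is the mean change without treatment, in SDs of the change, and is the same in both groups. There were 20,000 simulated runs per setting.

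**Why drift affects one test and not the other.** The mean change in one group has standard error 1/√n, which is 1/√25 = 0.20 at n = 25. A drift of 0.5 SD then lies 0.5/0.20 = 2.5 standard errors from zero with no treatment effect. In the between-group contrast the expected difference is d − d = 0.

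**No treatment effect, 25 per group:**

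| Shared drift (SD of change) | Within-group Wilcoxon rejects |
|---|---|
| 0 | 5.0% |
| 0.1 | 7.6% |
| 0.2 | 15.2% |
| 0.3 | 28.4% |
| 0.5 | 64.8% |

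For 14 to 40 per group, the within-group rate runs from 16.8% to 43.1% at 0.3 SD and from 39.6% to 85.3% at 0.5 SD. The Mann-Whitney test rejects in 4.1% to 5.1% of runs across these settings. At n = 25 the within-group test alone is significant in 26.2% of runs at 0.3 SD and 62.1% at 0.5 SD. These are the cases in which the missing priority matters.

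**Treatment exactly cancels a 0.5 SD drift, 25 per group.** The within-group test rejects in 4.9% of runs and the between-group test in 39.0%.

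**Cost in power.** With no drift and a true shift of 0.5 SD at n = 25, the between-group standard error is √(2/25) = 0.283. The shift is then 0.5/0.283 = 1.77 standard errors, against 2.5 within group. Simulated power:

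| n per group | Between-group Mann-Whitney | Within-group Wilcoxon |
|---|---|---|
| 14 | 22.0% | 39.3% |
| 25 | 38.7% | 64.7% |
| 40 | 57.0% | 85.3% |

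**The case against.** **The controlled analysis is already planned.** This stands, and it limits the point. A repeat scan of the controls has little purpose except to compare change. A reader might infer that the trial has no controlled morphology analysis, or that the plan makes the within-group result decisive. The documents support neither. The linking word that introduces the between-group test is ordinary prose used throughout the protocol, and does not show that the test is subordinate. The plan also marks the first test, in brackets, as within-group. What remains is that no priority is stated for a set of primary outcomes, while the uncontrolled test is the one described as evaluating treatment effects.

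**The design already limits drift.** In part. Physical therapy frequency must be stable for three months before inclusion, the same assessor performs both assessments, and "muscle volume will be normalized to the product of body mass*height". These steps reduce drift but do not exclude it. The normalization does not apply to echogenicity or absolute growth rate.

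**The drift values are invented.** They are assumptions. A reader might infer from the table that a 65% false-positive rate is expected, but nothing in the documents supports 0.5 SD over 8 to 10 weeks. For normalized volume and echogenicity even the direction of drift is unknown. At 0 to 0.1 SD the error rate is 5% to 8%, close to nominal. It would likewise go too far to say that the plan will report slowed growth as a gain: the growth rate has no named test, and normalized volume has no known drift.

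**The 5% rate for the between-group test is built in.** Correct. The simulated groups differ in nothing but treatment, whereas the real controls are non-randomised and their final data are selected by matching after measurement. The contrast removes change shared by the groups, not differences in selection.

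**The growth-rate gap is small.** Agreed. Over a near-constant interval the rate is almost a rescaled difference in volume, so naming its test is mostly clarification.

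**Conclusion.** The point holds in a limited form and is minor to moderate. Section 5 uses an uncontrolled test to evaluate treatment effects on muscle morphology and does not say that the planned comparison with controls decides the conclusion. That follows from the text and needs no assumed drift. The size of the consequence does: there is no excess error at zero drift, and about 8% to 65% false positives at a shared drift of 0.1 to 0.5 SD with 25 per group. The figure of about 5% for the between-group test requires groups that are otherwise comparable.

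The point is confined to morphology. Controls have no follow-up gait or instrumented spasticity data, so no control comparison could decide those outcomes.

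**What to change.** Add to section 5:

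1. Conclusions about treatment effects on muscle morphology, including the growth rate, rest on the between-group comparison of change.
2. The growth rate is compared between groups by the Mann-Whitney test.
3. Within-group Wilcoxon results for morphology are supportive, and are not by themselves evidence of a treatment effect.
4. The contrast is read as the effect of the integrated treatment, in line with the aim under Participants ("Both studies will investigate the effect of integrated BoNT-A treatment on muscle morphology and gait"), against a non-randomised matched control group.

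This needs no new data, because the control scans and the test are already planned. The cost is the lower power shown above. A non-significant between-group result must therefore not be read as no effect.
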